### **Softwares prediction different computational strategies**

The orthognathic planning softwares use several computational strategies (models) to generate soft tissue predictions based on the bone-related planning. These four strategies are: a linear Finite Element Model (FEM), a non-linear Finite Element Model (NFEM), a Mass Spring Model (MSM) and a novel Mass Tensor Model (MTM) Molleman's et al For true validation of these four models we acquired a data set of 10 patients who underwent maxillofacial surgery, including pre-operative and post-operative CT data. For all patient data we compared in a quantitative validation the predicted facial outlook, obtained with one of the four computational models, with post-operative image data. During this quantitative validation distance measurements between corresponding points of the predicted and the actual post-operative facial skin surface, are quantified and visualized in 3D. The results showed that the MTM and linear FEM predictions achieve the highest accuracy. Furthermore, the MTM turned out to be the fastest model, with an average simulation time of only 10 s. Besides this quantitative validation, a qualitative validation study was carried out by eight maxillofacial surgeons, who scored the visualized predicted facial appearance by means of predefined statements. This study confirmed the positive results of the quantitative study, so we can conclude that fast and accurate predictions of the post-operative facial outcome are possible. Therefore, the usage of a maxillofacial soft tissue

prediction system is relevant and suitable for daily clinical practice. Our results show that the MTM achieves the same accuracy as the linear FEM, but clearly beats MSM and the linear FEM in simulation time. No significant improvement of the simulation accuracy was found, when using the non- linear FEM. The validation study denotes moreover an acceptable error of the predictions for the MTM and linear FEM when quantitatively measuring distances between the predicted and real post-operative facial outlook. These positive results were confirmed by the qualitative validation study, so that we are able to conclude that maxillofacial soft tissue prediction systems can be used in daily clinical practice. (3)

**The 3D color maps** permit an objective analysis of the craniofacial structures. The method facilitated the evaluation of orthognathic surgery(61), reconstructive surgery(62),orthodontics(1), growth(63), and creation of facial templates(64). **A 3D color map** is a graphical qualitative and quantitative representation of the distance differences between 2 superimposed 3D images. Currently, most of the software compatible with 3D imaging data has the capability of generating color maps.(64) Color maps provide a qualitative methods of visualizing quantitative changes in skeletal position(63).

In the current study the research team try to formulate a complete surgical planning and prediction protocol that can pair the usage of recent methods of surgical planning, prediction, and assessment with the most reasonably priced service to allow treatment of patients with class II facial deformity in our developing country.

## **The Aim**

The aim of the present study is to evaluate the accuracy of Dolphin 3D software in the prediction of facial soft tissue changes after bimaxillary orthognathic surgery.

### ***Study Hypothesis***

There will be no difference between actual soft tissue results and Dolphin 3D software soft tissue prediction.

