### **3D Virtual planning and prediction:**

The limitations of the Two-dimensional (2D) computer programs for cephalometric measurements and treatment prediction were widely used. Through the development of three-dimensional (3D) examination techniques and computerized analysis methods (Westermark et al. 2005) (20), the opportunity to make 3D computerized predictions of orthognathic treatments has arisen (Gateno et al. 2000, Gateno et al. 2003)(21,22) and authors started to compare the accuracy of both methods where the 3d virtual planning and prediction showed higher accuracy of the 3d than the 2d method. In 2017 Bengtsson et al conducted a prospective randomized blinded case controlled comparison study on Treatment outcome of orthognathic surgery comparing planning accuracy in computer-assisted two- and three dimensional planning techniques, the study showed a statistically significant difference between 3D and 2D prediction methods with an advantage for the 3D. There are several studies on accuracy of 3D planning techniques (Marchetti et al. 2006, Xia et al. 2007, Mazzoni et al. 2010, Tucker et al. 2010, Aboul-Hosn Centenero and Hernandez-Alfaro 2012, Zinser et al. 2012, Hsu et al. 2013)(23–29). The majority of these studies did not test the prediction only; they also assessed transference of planned movements to surgery (occlusal templates) (Xia et al. 2007, Tucker et al. 2010, Aboul-Hosn Centenero and Hernandez-Alfaro 2012, Zinser et al. 2012, Hsu et al. 2013)(24,26,28–30). Almost all of the comparable studies on 3D planning have set the level for linear success at <2 mm and showed high success rates (80%–100%) (Marchetti et al. 2006, Xia et al. 2007, Mazzoni et al. 2010, Tucker et al. 2010, Hsu et al.

2013)(23,24,26,29). Hsu et al (*Hsu et al. 2013*)(29) presented the largest number of studied subjects (n=65) and found a mean linear difference for the maxilla of 1.1 mm and for the mandible 1.0 mm so it stepped on the 2D limitations with proved higher accuracy.

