### **Comparing pre-operative and post-operative analyses:**

Assessing the accuracy of 3D surgical predictions compared to the actual postoperative result relies on similar techniques of superimposition to 2D, but the method of measurement is potentially more complex. To date, several methods of analysis have been reported including: (1) differences in distance of specific landmarks,(48,49) (2) differences

between all the 3D points of the two entire facial surface meshes,(50,51) and (3) differences between all the 3D points of the two facial surface meshes following division into predefined anatomical regions.(52) Quantitative analysis of each technique involves measuring the linear distances between specific landmarks or between all of the 3D points of the two 3D surface meshes. This can be performed taking into account the direction using the average distance difference, i.e. the signed difference, or irrespective of direction using the absolute Euclidean difference, and finally the root mean square (RMS) difference. The signed differences will cancel out positive and negative values, under-estimating the error; the absolute Euclidean difference will ignore the direction and only report the magnitude.

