### ***Sample size calculation***

Based upon the assumption that we need to reach 90% accuracy, in light of the results of Resnick CM et al (2016), the computed effect size for the accuracy of linear measurements was found to be (1.05), using alpha ( $\alpha$ ) level of (5%) and Beta ( $\beta$ ) level of (20%) i.e. power = 80%; the study will include 10 subjects. To compensate for 15% for the use of non-parametric tests; the final minimum estimated sample size will be 12 subjects. Sample size calculation was performed using G\*Power Version 3.1.9.2.

Patients to be included:

- a) Patients who have class III facial deformity to be corrected using bimaxillary orthognathic surgery.
- b) No medical problems that might interfere with general anesthesia or interfere with bone and soft tissue healing.

Patients will be excluded if:

- a) There are craniofacial anomalies including cleft lip/palate,
- b) Patient have previous maxillofacial operations or facial scars,
- c) Correction mandates multi-segment Le Fort I osteotomies,
- d) There are orthodontic appliances in place at the time of T1 records.
- e) Genioplasty is recommended for deformity correction.
- f) There is facial Asymmetry.

All the patients are consented for using their data in research purposes.

The CBCT scans of class III patients who undergone maxillary advancement with minimal or without impaction and mandibular setback will be identified. The preoperative and 6 months postoperative CBCT images will be anonymized and will be saved in a password protected computer. Only the research team members will have access to the research data.

In order to quantify the actual amount of surgical movement, the pre and post-operation CBCT voxel based super imposition using ONDEMAND 3d. The surgical movement will be quantified using direct slice land-marking.

Using the pre-operation CBCT to do the surgical mock up and the soft tissue simulation on dolphin 3D. Soft tissue surface models of the simulation and the actual postoperative images will be generated and exported as STLs.

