### **Data Analysis**

Superimposition of the predicted and the post-operative STLs and conformation of the generic meshes will be performed. Using VR mesh software, the mesh will be segmented into pre-identified anatomical regions. The distance between the corresponding vertices will be displayed

as a colour scale in milli-meter and will be analyzed in the individual dimension of space (x, y and z) using in-house software developed for this purpose and each dimension will be displayed as a colour coded distance map. It will be generated to illustrate the magnitude and anatomical regions with prediction inaccuracies analysis. Using this software, the minimum, maximum, mean, standard deviation (SD), absolute maximum, absolute mean, and absolute SD of 90% of the points of each facial anatomical region will be measured.

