### ***Statistical analysis***

Numerical data will be explored for normality by checking the distribution of data and using tests of normality (Kolmogorov-Smirnov and Shapiro-Wilk tests). Data will be presented as mean, median, standard deviation (SD), minimum, maximum and 95% Confidence Interval (95% CI) for the mean values. For parametric data, paired t-test will be used to compare between actual soft tissue measurement and software measurement. For non-parametric data, Wilcoxon signed-rank test will be used to compare between actual soft tissue measurement and software measurement. Inter- and intra-examiner reliability will be assessed using Cronbach's alpha and Intra-Class Correlation coefficients.

The significance level will be set at  $P \leq 0.05$ . Statistical analysis will be performed with IBM® SPSS® Statistics Version 20 for Windows.

---

\* IBM Corporation, NY, USA.

\* SPSS, Inc., an IBM Company.

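### The study aims at accuracy, but its only test of actual against predicted is a paired difference test that cannot support 'no difference', and no limit in mm is set for judging the planned error estimates

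*Combined protocol and SAP*

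**What the plan says.** All places are in the combined protocol and SAP.

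- **The Aim:** the purpose is to "evaluate the accuracy of Dolphin 3D software in the prediction of facial soft tissue changes after bimaxillary orthognathic surgery", a question of accuracy.
- **Study Hypothesis:** the section is a single sentence, "There will be no difference between actual soft tissue results and Dolphin 3D software soft tissue prediction". No margin is attached.
- **Statistical analysis:** for parametric data, a "paired t-test will be used to compare between actual soft tissue measurement and software measurement"; for non-parametric data, the Wilcoxon signed-rank test makes the same comparison. The significance level is 0.05. Means are to be reported with 95% confidence intervals.
- **Data Analysis:** corresponding vertices of the predicted and postoperative surfaces are compared, overall and along x, y and z. Summaries are both signed and absolute, including the "absolute mean, and absolute SD of 90% of the points of each facial anatomical region will be measured".
- **Sample size calculation:** it opens "Based upon the assumption that we need to reach 90% accuracy" and continues that "the computed effect size for the accuracy of linear measurements was found to be (1.05" in standardised units. With alpha 5% and power 80% this gives 10 subjects, raised to a minimum of 12 by a 15% allowance for non-parametric tests.
- **3D Virtual planning and prediction** (literature review): "Almost all of the comparable studies on 3D planning have set the level for linear success at <2 mm". The methods sections do not adopt this level.

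**The concern.** A difference test answers whether there is evidence that the mean difference is not zero. An accuracy study asks whether the error is small enough. Taken as a null hypothesis, the stated hypothesis can only be rejected or not rejected. Taken as a claim, this test cannot confirm it.

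The quantities that could answer the accuracy question, the regional absolute errors with their intervals, are planned but have no benchmark. If the limit is chosen once the results are known, it can be fitted to them.

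It is also unclear what the test will be run on. Data Analysis produces distances between the two surfaces, which are already differences. Statistical analysis compares an actual measurement with a software measurement and names neither.

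**Working it through.** **Inputs from the documents.** Effect size 1.05, alpha 5%, power 80%, n = 10 raised to 12 (Sample size calculation); paired t-test at 0.05 (Statistical analysis). Neither a mean difference nor an SD is given in mm, so results below are in units of the between-patient SD of the paired difference. I assume a two-sided test and normal differences. The Wilcoxon test was not computed.

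**Step 1: the plan's own figure.** Power of a two-sided paired t-test is P(|T| > t(0.975, n−1)), where T is noncentral t with n−1 degrees of freedom and noncentrality d√n. For d = 1.05:

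| n | power |
|---|---|
| 9 | 78.7% |
| 10 | 83.9% |
| 12 | 91.1% |

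So 10 reproduces. The allowance gives 10 × 1.15 = 11.5 or 10 / 0.85 = 11.8, and both round up to 12.

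**Step 2: does that N show what the study was sized for?** An equivalence design (two one-sided tests, 5% each, margin 1.05 SD, true difference 0) has 77.9% power at n = 9 and 84.2% at n = 10. It also needs 10. The sample size text names no test, so N alone does not separate the two designs.

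**Step 3: how the paired test behaves at n = 12.** The same formula with t(0.975, 11) = 2.201 gives:

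| True mean difference | Noncentrality d√12 | Significant | Not significant |
|---|---|---|---|
| 0.5 SD | 1.73 | 35.3% | 64.7% |
| 1.0 SD | 3.46 | 88.3% | 11.7% |

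Only the ratio of offset to SD enters. As an illustration with assumed values, a 0.2 mm offset with SD 0.2 mm and a 3 mm offset with SD 3 mm are both flagged 88% of the time.

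Conversely, if patients' differences average zero, the test is non-significant 95% of the time at any scatter. With zero-mean normal differences the mean absolute error is SD × √(2/π). For assumed SDs of 1, 2 and 3 mm that is 0.8, 1.6 and 2.4 mm, and the test behaves identically in all three cases.

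**Step 4: is there a limit anywhere?** The figure below 2 mm describes other 3D planning studies. The 90% accuracy target has no unit or tolerance and does not reappear in Data Analysis or Statistical analysis. No equivalence margin, limits of agreement or success rule is given.

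**Step 5: what a bound against a limit would demand of 12 patients.** Let L be the limit, and m and s the observed mean and SD of the per-patient error. The rule is m + t(0.95, 11) × s/√12 < L. Since 1.796/3.464 = 0.518, m must lie about 0.52 SD below L. The chance of passing, from a one-sided noncentral t with noncentrality k√12, and the smallest n giving at least 80%, are:

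| True mean below L by | Chance at n = 12 | n for 80% |
|---|---|---|
| 0.5 SD | 0.4919 (49%) | 27 |
| 0.75 SD | 0.7848 (78%) | 13 |
| 1.0 SD | 0.9447 (94%) | 8 |

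**The case against.** The best defence is that the aim is to evaluate accuracy, not to declare the software accurate, and that the plan is well equipped for this. Absolute errors by region, colour maps by axis, and means with 95% confidence intervals all estimate the size of the error. This stands. A reader might infer that the study cannot answer its question at all; the planned estimates show otherwise. What remains is that the formal hypothesis and its test do not bear on accuracy, and that the estimates have no prespecified yardstick.

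Three other strong readings are tempting and not supported:

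- **That the sample size proves the study was built to find a difference.** An equivalence test with a margin of 1.05 SD needs the same 10 subjects. The analysis section makes a difference test the likelier reading, but N does not establish it.
- **That the plan's own background condemns the paired test.** The text says "The signed differences will cancel out positive and negative values, under-estimating the error", but there and under Analysis based on surface meshes the cancellation is across points of one facial mesh. The absolute summaries already planned deal with it. Cancellation between patients (Step 3) follows from how a paired test works and is a separate point.
- **That the team will report P above 0.05 as accuracy.** The plan does not say how such a result will be read.

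It is also fair that the mm examples rest on assumed SDs. They show what is possible, not what is likely here.

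**Conclusion.** The point holds in this form: the only inferential comparison cannot support the stated hypothesis, its P-value does not track accuracy, and the estimates that do measure accuracy lack a limit fixed in advance. The size, under normality and a two-sided test on one difference per patient, is 65% non-significance at a true difference of 0.5 SD and 88% significance at a consistent 1 SD offset. Those percentages need no SD in mm; translating them into mm does. The sample size arithmetic is not at fault. Which variable enters the paired test is unstated and has to be settled whatever else is decided.

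**What to change.** Before analysis:

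1. Name one primary measure with one value per patient, for example the absolute mean distance between corresponding vertices in one named region, which Data Analysis already produces. The background's warning about cancellation within a mesh is the reason to prefer the absolute form.
2. Fix and justify a soft-tissue accuracy limit in mm. Define the 90% accuracy target or delete it.
3. Replace the hypothesis with one that the mean error is below the limit. Regard it as supported only if the one-sided 95% upper confidence bound of the mean lies below the limit. Report other regions and axes descriptively with confidence intervals.
4. Keep the paired test only to describe systematic bias, name the variable it uses, and state that P above 0.05 is not evidence of accuracy.

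**Cost.** The hypothesis and statistical section are reworded, and one measure and one limit must be chosen and defended. The planned measurements already supply the data. Accuracy becomes harder to claim, and 12 patients may be too few for a clear answer (Step 5), which the plan should say openly. The plan calls 12 a minimum and uses existing scans, so more patients could be added if suitable scans exist.

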## **Patients and Methods**

This will be a retrospective study to investigate the accuracy of Dolphin 3d software for the prediction of post-operative soft tissue changes following bimaxillary orthognathic surgery to correct class III jaw defects through combined maxillary advancement and mandibular setback. The study will employ the pre-existing CBCT images routinely captured for orthognathic surgery patients in Glasgow dental hospital and school. Then difference between the pre-operative soft tissue prediction and the 6-month postoperative results will be analyzed. The study will be conducted in Glasgow dental school and hospital using patients pre-existing data after the ethical approval.

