As the facial surface mesh is made up of thousands of points, an overall mean value for the error is often reported. If one facial surface mesh is totally in front of the other, all the distance measurements will be either positive or negative and therefore the mean is valid. If however some parts of one mesh lie behind and some in front of the other mesh, distance measurements for the whole face will be made up of positive and negative values. Any positive values will cancel out any negative values under-estimating the mean difference and so biasing the results. In order to overcome this problem, some studies use the absolute mean values or Euclidean distances, which ignore the sign (direction) and report on the magnitude of error or the RMS error. The RMS error is derived from all the points making up the surface mesh which makes it not clinically useful, as the site of the error remains unknown; however, dividing the face into anatomical regions and analyzing them separately immediately focuses on

the areas of error. Many studies assess the accuracy of the prediction by comparing the differences in distance between the prediction and the actual surfaces using the entire face, including the areas that have been used for alignment, i.e. the areas with minimal change. Therefore a large percentage of the mesh has minimal or no change; this will bias the accuracy by reducing the impact of the error—the data will be skewed towards the smaller values. In order to overcome this, areas of the face used for alignment can be excluded and the remaining mesh divided into anatomically relevant regions this method highlights the true level of error in the predictive ability of the package.

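### Prediction error is not set against how much the soft tissue changed, so in low-movement regions or axes a small error does not show the software did better than the unaltered pre-operative face

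*Combined protocol and SAP*

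**What the plan says.** The Aim is to "evaluate the accuracy of Dolphin 3D software in the prediction of facial soft tissue changes after bimaxillary orthognathic surgery". The contrast to be used is given in Patients and Methods: the "difference between the pre-operative soft tissue prediction and the 6-month postoperative results will be analyzed". As for the Study Hypothesis, it is "There will be no difference between actual soft tissue results and Dolphin 3D software soft tissue prediction"; it sets no margin and names no comparator.

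The measurement steps involve two surfaces:

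- Sample size calculation (the imaging steps sit under this heading): "Soft tissue surface models of the simulation and the actual postoperative images will be generated and exported as STLs".
- The registration step, described under Data Analysis, reads: "Superimposition of the predicted and the post-operative STLs and conformation of the generic meshes will be performed". The mesh is then divided into pre-identified regions. Signed and absolute distances are summarised over 90% of the points in each region, and each axis is mapped separately.
- Statistical analysis: a paired t-test, or the Wilcoxon signed-rank test, compares the actual with the software measurement. Neither measurement is defined further.

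The pre-operative CBCT is used to build the simulation and, with the post-operative scan, to quantify surgical movement by landmarking. No analysis step relates that movement to prediction error, and none states a pre-operative-to-6-month soft tissue distance.

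The literature review (Analysis based on surface meshes) warns about whole-face analyses that include the alignment areas, because "a large percentage of the mesh has minimal or no change". Its remedy is to leave out the alignment areas and analyse the rest by region.

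**The concern.** An error in millimetres has no meaning on its own. An error of 1 mm is informative where the lip moved 6 mm. Where it moved 1 mm, leaving the pre-operative face untouched could have done as well. The plan reports the error and not the movement, so a reader cannot tell these cases apart.

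Low-movement comparisons are likely here. The operation is maxillary advancement with little or no impaction plus mandibular setback, and asymmetric faces are excluded. The intended bony movement is therefore mainly anteroposterior, yet x, y and z are each examined. Small vertical or transverse errors may largely reflect small movement. The risk is that agreement in such regions or axes is credited to the software.

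**Working it through.** **1. The plan's own figure.** Inputs from Sample size calculation: effect size 1.05, alpha 5%, power 80%. For a two-sided paired t-test (noncentral t), n = 9 gives power 0.787 and n = 10 gives 0.839, so 10 is reproduced. The 15% allowance gives 10/0.85 = 11.76 or 10 × 1.15 = 11.5; both round up to 12. The sample size arithmetic is not at issue.

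**2. What the planned distance measures.** At any vertex,

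predicted − actual = (predicted − pre-operative) − (actual − pre-operative).

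The shared baseline cancels, so the planned distance is the error in predicted change. For software that predicts no change, predicted = pre-operative, and the error equals the actual change with its sign reversed. Its error is therefore small wherever the change is small.

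**3. How often the paired test would miss no-change software.** The documents give no soft tissue change or SD, so the values below are assumptions. Assume one signed, normally distributed regional value per patient, n = 12, and a two-sided test at 0.05. The noncentrality is (mean/SD) × √12 on 11 degrees of freedom. The probability of a non-significant result is:

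| Mean change | SD 1 mm | SD 1.5 mm | SD 2 mm |
|---|---|---|---|
| 0.5 mm | 65% | 82% | 88% |
| 1 mm | 12% | 44% | 65% |
| 2 mm | <0.1% | 1% | 12% |
| 3 mm | <0.1% | <0.1% | 0.3% |

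Simulation at SD 1 and 2 mm agreed (for example 64.6% at 0.5 mm/SD 1 and at 1 mm/SD 2).

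Power is 50% at a standardised mean of 0.62 and 80% at 0.89. No-change software would thus escape more often than not when mean change is below 0.62 × SD: 0.62, 0.93 and 1.24 mm for SDs of 1, 1.5 and 2 mm. Hence roughly 1 mm or less.

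**4. Illustration with a 2 mm limit.** Some cited planning studies "have set the level for linear success at <2 mm". This study does not adopt that limit. If it did, the share of patients in whom the untouched pre-operative face passes would be Φ((2 − m)/s) − Φ((−2 − m)/s), for mean change m and SD s:

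- m/s = 1/1 mm: 0.840
- 2/1.5 mm: 0.496
- 3/1.5 mm: 0.252
- 4/2 mm: 0.157

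Only the first reaches the 80% to 100% success quoted from those studies.

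**5. Precision of the proposed comparison.** The 95% CI half-width for a paired mean difference at n = 12 is 2.201 × SD/√12 = 0.635 × SD. That is 0.64 mm for SD 1 mm and 1.27 mm for SD 2 mm (assumed).

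**The case against.** The strongest reply is that absolute agreement is the question asked, and the planned distances answer it. That stands. A reader might infer that the analysis ignores change and so cannot address the aim. Step 2 shows otherwise: the simulation and the outcome share a baseline, so the distances are errors in predicted change. Superiority to a no-change prediction is a further question that the protocol does not pose. It is still needed to interpret a small error.

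Second, the literature review's warning concerns whole-face summaries, and Data Analysis already adopts regional division. This stands in part. Data Analysis does not state that alignment areas are excluded, and regions alone give no benchmark inside a region that moved little.

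Third, every patient has both jaws moved, and at larger movements the planned test would expose no-change software. This stands and limits the point. Part of the difficulty also lies elsewhere, in reading a non-significant test as agreement without a margin; a comparator does not cure that.

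Fourth, the compared measurements are undefined in Statistical analysis and could be changes from baseline. That is possible, but no step produces a pre-operative soft tissue surface from which to derive them.

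Finally, a per-patient ratio of error to change would be unstable where change is near zero, which is the case of interest. This is correct, and the fix avoids it.

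**Conclusion.** The point holds in a limited form. The plan measures error in predicted change but gives no reference for the size of the change. In regions or axes with mean movement of roughly 1 mm or less, neither a small distance nor a non-significant test in 12 patients shows benefit over the unaltered pre-operative face. This rests on assumed SDs of 1 to 2 mm, normality and one signed value per patient. The absence of a comparator does not depend on those assumptions.

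Two stronger readings are not supported. One is that software predicting no change would generally be found accurate; at 3 mm mean change it would escape the test in at most 0.3% of studies. The other is that a no-change prediction would meet this study's success criterion. The study sets no such criterion, and the 2 mm level comes only from cited planning studies. The planned results remain usable, and the change is a worthwhile, inexpensive improvement.

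**What to change.** Before analysis, add the following to Data Analysis and Statistical analysis:

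- Export the pre-operative soft tissue surface from the CBCT already held, register it in the same frame as the other two surfaces, and conform the same generic mesh.
- For each patient and pre-identified region, report (a) the predicted-to-actual absolute mean distance and (b) the pre-operative-to-actual absolute mean distance.
- Give the paired difference (b) − (a) with its 95% CI as a pre-specified secondary estimate. Positive values mean that the software improved on no prediction.
- Do not use a per-patient ratio. At most, give a ratio of group means for regions with material change.
- State that alignment areas are excluded.
- Plot (a) against the measured surgical movement, descriptively.

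The cost is about 12 extra surface exports, registrations and conformations, with the matching regional segmentation, and one more table. No new patients or scans are needed. Intervals will be wide at n = 12, so the comparison should be reported as an estimate rather than as a further set of significance tests.
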